Monthly Doront	family members living in the home). The MacArthur-Bates Communicative Development Inventories (MCDI): Words and Gestures or Words and Sentences (the parent selects which words their child says and understands out of 680 words). English, Spanish, and American Sign Language versions (if applicable) Use of Community-Based Intervention	Parent	60 min.	Home	Monthly
Monthly Parent Surveys/Interviews	Services and Hearing Device Log (the parent answers questions about how many and what types of other therapy services their child received in the last month; indicates how often the child wears their hearing device across 8 different routines, such as meal times) Child's Communication – Survey about				
Visual Reception scale of the Mullen Scales of Early	child's communication The child is presented with different nonverbal tasks such as looking for a ring under a washcloth until the child fails to complete	Child	20 min.	Home or Lab	Post (T24)
Learning (MSEL) Goldman-Fristoe Test of Articulation – 3 rd edition (GFTA-3)	three consecutive tasks correctly. The GFTA-3 will take 20 minutes to administer. The GFTA-3 measures phonological skills by assessing an individual's articulation of the consonant and consonant cluster sounds of Standard American English. It provides information about an individual's speech sound ability by sampling both spontaneous and imitative sound production in single words and connected speech. GFTA-3 provides age-based normative scores separately for females and males for the Sounds-in-Words and Sounds-in-Sentences tests. Intelligibility is reported as a percentage score, and Stimulability information is reported in table format.	Child	20 min.	Home or Lab	Follow-up (T24)
Attention to Speech vs Sine-Wave Eye- Tracking Task	Children will be presented with two types of trials: speech sounds, and sinewave-transformed complex sounds. Once the child is attending to the screen, a trial will begin. Children will see either a red and white checkerboard pattern or a red and white bullseye. On speech trials, children will hear a random sequence of syllables ("lif" and "neem"). On sinewave trials,	Child (Chicagolan d participants only)	5 min.	Lab (if allowed by the state)	Pre (T0)

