Multicollinearity. This proposal includes a large set of prelinguistic and linguistic variables, some of which will be included in the same analyses. Our data reduction is one part of our solution to multicollinearity, such that latent constructs that account for shared variation between comparable predictors will be used when possible. In other cases, we will control for multiple collinear variables in the same analysis, specifically when using multiple coded variables from naturalistic parent-child interactions. In those cases, we will use alternative decomposition and transformation methods. Principle components analysis (PCA) can transform a set of collinear predictors into a set of uncorrelated variables representing variance in the original data. For example, a simple PCA of one parent and one child variable would yield two components: one indicating shared family level behavior and the other representing scaled differences between parent and child. We will further explore non-linear transformations to make sure non-linear associations and distributional assumptions are accounted for, including both simple (e.g., polynomial or logarithmic transformations to improve distributions) and complex (e.g., adjusting observed child communication for proportion of time spent communicating) transformations. This set of methods integrates well within our SEM framework and multivariate longitudinal design.

Missing data. Given this is an intent-to-treat trial, all 96 children randomized will be included in the analyses of primary outcomes even if data are missing. However, our preliminary studies showed high retention rates (e.g., 95% retention in the pilot study - R03DC012639), but missing data occurs in all longitudinal studies. All models will be estimated using full information maximum likelihood (FIML), which uses all available data and yields unbiased parameter estimates under the most common missingness mechanisms. We will further use our set of predictors and covariates to predict missingness, and include those variables as covariates to conform to FIML assumptions. For non-ignorable missing data, we will conduct sensitivity analyses using non-ignorable pattern-mixture and selection models to investigate the robustness of our conclusions across the different models for missing data.

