Covariates. Controlling for covariates is an important part of any analysis. While randomization and stratification should remove effects of these variables, additional statistical control curtails potential unhappy randomizations and other threats to internal validity. As such, we will examine differences between experimental conditions for the following variables: non-verbal cognitive skills, degree of hearing loss in the better ear, hearing age, hours of hearing device use, SES, sign exposure in the home, other spoken languages in the home and amount of community-based early intervention therapy services. Should a difference exist at any point in the study, we will include that variable in all statistical analyses.

Multiple testing. Our proposed analyses and rich multivariate data collection will allow us to test hypotheses in multiple ways. Our focus on SEM will allow for complex hypotheses to be tested with a single model, obviating part of the need for multiple testing corrections. However, we will further employ Benjamini-Hochberg corrections⁸⁸ as needed to correct for multiple testing. This procedure is a more sophisticated alternative to traditional Bonferroni corrections that better account for multiple simultaneous significant parameters.

[figure not shown]
Aim 1 Analyses

This aim tests the main effects of the intervention, both on parental use of communication support strategies and on child prelinguistic skills. We predict that: (a) parents in the intervention group will use more communication support strategies during intervention than parents in the control group (analysis 1.1); (b) children in the intervention group will have greater growth in rate of prelinguistic communicative acts between 12 months (pre) and 18 months of age (post) (analysis 1.2a) and greater overall prelinguistic skills at 18 months of age (post) (analysis 1.2b) than children in the control group. We will employ a mix of traditional and advanced statistical methods, balancing simplicity of linear regression and related methods with sophisticated SEMs that handle attrition and missing data and allow for more flexible integration of time-varying covariates.

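### The SAP's covariate rule lets post-randomisation variables into the Aim 1 and Aim 3 treatment-effect models; if PICT changed such a variable, the estimate is no longer the intention-to-treat effect

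*SAP*

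**What the plan says.** The SAP's Covariates paragraph names non-verbal cognition, degree of loss in the better ear, hearing age, and "hours of hearing device use, SES, sign exposure in the home, other spoken languages in the home and amount of community-based early intervention therapy services". The arms are to be compared on these eight, and "Should a difference exist at any point in the study, we will include that variable in all statistical analyses". The reason given is chiefly chance imbalance at randomisation, with a general reference to other threats to validity. The paragraph sets no threshold for a difference and does not say which measurement of the variable enters.

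Three other places bear on how the rule would work.

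- SAP, Aim 1 Analyses, says the SEMs "allow for more flexible integration of time-varying covariates". The Aim 3 section says the same.
- SAP, Missing data: "We will further use our set of predictors and covariates to predict missingness, and include those variables as covariates to conform to FIML assumptions". This has no baseline restriction either.
- The same paragraph sets the analysis principle: "Given this is an intent-to-treat trial, all 96 children randomized will be included in the analyses of primary outcomes".

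Protocol section 8.0 places randomisation after the baseline assessments, so every T1 to T24 value is post-randomisation. In its Table 1, the monthly parent survey records "how many and what types of other therapy services their child received in the last month" and "indicates how often the child wears their hearing device across 8 different routines, such as meal times". The language-exposure interview is held at T0 and repeated at 24 and 36 months of age. Cognition is covered by a parent-report ASQ at T0, a second parent report at 24 months of age, and the "Visual Reception scale of the Mullen Scales of Early" Learning, a direct test listed only at T24.

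**The concern.** A covariate measured before randomisation cannot be affected by treatment, so adjusting for it leaves the meaning of the treatment coefficient intact. A covariate measured afterwards can be affected. The rule selects exactly those variables on which the arms have diverged, which includes any that diverged because of PICT. Putting such a value in the model conditions on a consequence of treatment.

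The direction is not known in advance. If PICT raises something helpful, such as device use, adjustment removes part of the real effect. If control families obtain more helpful outside services, adjustment inflates the effect. The rule therefore cannot be defended as conservative.

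Four of the eight variables are measured after randomisation and could plausibly respond: device use, community services, sign exposure and non-verbal cognition. Degree of loss, hearing age, SES and other home languages are unlikely to.

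There is also a timing problem. A trigger at any time, applied to all analyses, leaves the covariate set for the T7 models open until T24. A cognition difference on the T24 Mullen would bring that variable into the T7 CSBS regression, 24 − 7 = 17 months after the endpoint if the T24 score is used.

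**Working it through.** **Inputs from the SAP (Power Analysis).** Analysed n = 86; 80% power at d = 0.61, 90% at 0.71, above 99% at 1.07; with n = 96, 80% at 0.58 and 90% at 0.67.

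**Assumed, because the documents do not give them.** 1:1 allocation (43 per arm); two-sided alpha 0.05; a p < 0.05 trigger for a difference; a = shift in the covariate caused by PICT (SD); b = within-arm slope of the outcome on the covariate (SD per SD).

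**Step 1: reproduce the plan's power.** Two-sample noncentral t, df = 84, noncentrality = d × √(43 × 43 / 86) = 4.637d.

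- n = 86: d = 0.61 gives 79.8%, 0.71 gives 90.2%, 1.07 gives 99.8%.
- n = 96: d = 0.58 gives 80.3%, 0.67 gives 90.1%.

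All the stated figures reproduce. A one-sided test does not fit (88% at 0.61).

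**Step 2: effect of adjusting.** Let M = a × arm + e₁ and Y = (τ − ab) × arm + bM + e₂, with within-arm SD 1 for both. The total effect is τ. The coefficient for arm with M in the model is τ − ab. With τ = 0.61:

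- a = 0.3, b = 0.3: 0.61 − 0.09 = 0.52
- a = 0.5, b = 0.3: 0.61 − 0.15 = 0.46
- a = 0.5, b = 0.5: 0.61 − 0.25 = 0.36
- a = −0.3, b = 0.3: 0.61 + 0.09 = 0.70
- a = −0.5, b = 0.3: 0.61 + 0.15 = 0.76

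M need not itself affect Y. If the two only share an unmeasured cause (loadings 0.5 and 0.5, so a within-arm slope of 0.25), a = 0.5 gives 0.61 − 0.125 = 0.485; the simulation gave 0.49.

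**Step 3: the conditional rule, simulated.** b = 0.3, 43 per arm, OLS. M enters only if a t-test on it gives p < 0.05 at one look, or at any of seven monthly looks T1 to T7 (within-child correlation 0.8, last value entered). Cells show the mean estimate, with the rejection rate in brackets where quoted. Repeat runs agreed to about 0.01 in the estimate and 2 percentage points in power.

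| a | Always adjusted | One look | Seven looks |
|---|---|---|---|
| 0 | 0.61 (83%) | 0.61 | 0.61 |
| 0.1 | 0.58 (78%) | 0.60 (80%) | 0.59 (78%) |
| 0.2 | 0.55 (74%) | 0.59 (77%) | 0.57 (76%) |
| 0.3 | 0.52 (69%) | 0.57 (74%) | 0.55 (72%) |
| 0.5 | 0.46 (57%) | 0.49 (61%) | 0.47 (57%) |
| −0.3 | 0.70 | 0.65 | 0.68 |
| −0.5 | 0.76 | 0.73 | 0.75 |

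At a = 0.5 the variable entered in 63% of trials with one look and 84% with seven.

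**Step 4: type I error when the total effect is zero.** With a = ±0.5 the adjusted estimate centres on ∓0.15. Rejection is 11% always adjusted, 9% with one look and about 10% with seven. At a = 0.3 the conditional rule gives 5.4% and 6.2%. At a = 0.1 to 0.2 it stays near 5%, and at a = 0 it is 5%.

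**Step 5: how open the covariate set is, with no PICT effect on any variable.** Eight independent variables at one look: 1 − 0.95⁸ = 34% chance that at least one enters. One monthly variable: about 15% over seven looks and 24% over 25. This leaves the model undetermined but does not bias it.

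**The case against.** The best defence is that the T0 value is meant. The paragraph's main purpose is to guard against an unlucky randomisation, it says only that the variable is included, and the remark on time-varying covariates describes what SEMs can do without naming a model. On that reading there is no bias. But the SAP does not say so, and a trigger at any time fits poorly with chance imbalance, which is already present at T0. Two analysts could follow the sentence and estimate different quantities.

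Several further objections limit the size of the problem.

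- PICT teaches visual, interactive, responsive and linguistic strategies; device wear, signing and use of services are not among those listed. An effect on them is an inference, as is treating the wear log across routines as hours of use.
- A shift of 0.5 SD is large beside a target effect of 0.61. At 0.1 to 0.2 the conditional rule costs little. With a = +0.5, the null case also needs a direct PICT effect of −0.15 that exactly cancels the indirect benefit.
- The simulation is a single regression without a pre-test term, so it approximates analyses 1.2b and 3.2b. No size has been worked out for the growth-slope analyses 1.1, 1.2a, 3.1 and 3.2a.
- Protocol section 19.0 expects the aims to be completed only once all longitudinal data are in, and section 17.0 keeps outcomes by arm out of interim reports. The open covariate set is therefore less harmful in practice than it sounds.
- Table 1 labels the Mullen row as post but dates it T24, whereas post is T7 elsewhere. The 17-month example depends on the T24 date.
- The missing-data sentence could be read as describing auxiliary variables.

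All of these reduce the certainty or size of the bias. None supplies the missing restriction to baseline values.

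**Conclusion.** The concern holds and should be corrected before analysis. As written, the rule permits covariates that are consequences of treatment in every Aim 1 and Aim 3 model, and the SAP describes no unadjusted or baseline-only fallback. Bias arises only if a post-baseline value enters, PICT changed it, and it is associated with the outcome within arms. Under those conditions the estimate moves by ab in either direction: 0.09 SD (15% of 0.61) for a = 0.3 and b = 0.3, and 0.15 SD (25%) for a = 0.5 and b = 0.3, when the variable is always entered. Conditional entry reduces this somewhat. These sizes rest on assumed a, b, trigger and allocation, and apply to the two regression analyses. That the wording allows such adjustment is clear; how large the bias would be in this trial is not known.

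**What to change.** In SAP, Covariates, replace the conditional sentence with a fixed set for the Aim 1 and Aim 3 models: the T0 value of the outcome, the two stratification factors (device status and communication mode), age at T0, and named T0 variables from the existing list. For cognition, use the T0 ASQ and not the T24 Mullen. State that no variable measured after randomisation is a covariate in a treatment-effect model.

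In SAP, Missing data, state that post-baseline predictors of missingness enter as FIML auxiliary variables and not as regressors.

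Report post-baseline device use, services and sign exposure by arm descriptively, or use them in exploratory mediation or labelled sensitivity analyses.

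The cost is wording in two paragraphs. The T0 measures are already scheduled. Baseline cognition is then parent-reported only, which controls less precisely than a direct test, and the strata and age use a few degrees of freedom. With baseline covariates a = 0 by design: in the simulation the adjusted estimate stayed at 0.61, with 83% power for a slope of 0.3 and 5% type I error.

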PROTOCOL TITLE:

Communication Intervention for Toddlers with Hearing Loss

PRINCIPAL INVESTIGATOR:

[name], CCC-SLP Communication Science and Disorders

CO-INVESTIGATOR:

[name]. Lurie Children's Hospital

VERSION DATE:

1.04.22

Page 1 of 20 Revised: May 25, 2018

1.0 Purpose of the study:

While children with hearing loss (HL) are experiencing greater gains in spoken language than ever before, considerable variability exists and many children with HL continue to have poorer language skills than their hearing peers. Critical to reducing this variability is the identification of: (a) effective early communication interventions for children with HL and (b) child and parent characteristics that influence intervention outcomes (moderators and mediators). However, to date, only the pilot study for this proposed study has directly examined the effects of an early communication intervention for children with HL within the context of a randomized clinical trial. The overarching goals of the proposed study are to: (a) evaluate the effects of teaching parents to use communication support strategies on child communication outcomes and (b) examine parent and child characteristics that moderate and mediate intervention outcomes. The central hypothesis is that systematic parent training will result in greater parental use of communication support strategies, greater child prelinguistic behaviors, and greater child spoken language outcomes. The specific aims include: (a) comparing parent use of communication support strategies and child prelinguistic outcomes between intervention and control groups during and immediately following intervention, (b) examining parent (communicative insightfulness) and child (sensitivity to social contingency; attention to spoken language) moderators of intervention outcomes; (c) comparing parent use of communication support strategies and child spoken language outcomes between intervention and control groups after intervention (from T7 to T24 months); and (d) examining parent (use of communication support strategies) and child (prelinguistic skills) mediators of intervention outcomes. The proposed study will enroll 96 children with mild to profound bilateral hearing loss.

2.0 Background / Literature Review / Rationale for the study:

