Social Engagement Eye-Tracking Task	The child participates in two consecutive engagement conditions with animal hand puppets as the stimuli: (a) joint attention, (b) unavailable. Each condition includes six trials (six different puppets coming out of an opening). In the joint attention condition, the caregivers will respond only after the child vocalizes or gestures by looking back and forth between the puppet and the child and talking about the puppet. In the unavailable condition, the caregiver will read a book silently and will ignore all child communicative behavior.	Child (Chicagolan d participants only)	5 min.	Lab (if allowed by the state)	Pre (T0)
Communicative Insightfulness Assessment	The parent watches video clips of their child and determines when and why their child is communicating.	Parent (Chicagolan d participants	30 min.	Lab (if allowed by the state)	Pre (T0)

Revised: May 25, 2018

		only)			
Word Learning Eye-Tracking Task	Children will be presented with 29 trials total. On the first two trials, children will be familiarized to the task by seeing two familiar objects on the screen and asked to find one of them. Children will then be presented with images of two novel objects in order to familiarize them with the objects. Following this, children will see 2 movies, each 24 seconds long, that teach the child the name for reach of those new objects ("blick" and "modi"). After this, children are presented with four blocks of test trials. In each test block, children are given 4 test trials in which they are asked to find one of the new objects, and two reminder trials, where the new objects are shown and named in isolation.	Child (Chicagolan d participants only)	6 min	Lab (if allowed by the state)	Follow-up (T24)
Audiology Record Requests	Audiology records will be obtained to confirm degree of hearing loss. The parent will be asked to sign a specific hospital release form, so that we can request the child's audiology records.	Parent	NA	NA	Pre (T0) Post (T7) Follow-up (T24)
	SLP/DTH M		T < 0	1	T =
Early Intervention Therapist Observation (SLP, DTH)	The parent and child will participate in their typical therapy session with their SLP or DTH in their home and the session will be video recorded.	Parent/Careg iver and Child and SLP or DTH	60 min.	Home	Beginning of study (~T4) End of study (~30 months old)

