This aim builds on the analyses of the first to identify moderators of intervention effects by way of SEM-based regression. Identifying moderators of intervention effects will allow us to better understand the effects of intervention and better identify factors that influence response to intervention. In Aim 2, we predict that: (a) parents who show greater insight regarding the intent of their child's prelinguistic communicative behaviors (have greater communicative insightfulness) at pre-test will have a larger intervention effect (2.1) and (b) children who associate their prelinguistic communicative behaviors with responses from their parents (have greater sensitivity to social contingency) at pretest (analyses 2.2a and 2.2b) and (c) have a greater attention to spoken language at pre-test will have a larger intervention effect (analyses 2.3a and 2.3b). Analysis 2.1 uses the proportion of child communicative acts that parents correctly identify (communicative insightfulness) as a moderator of a latent variable that describes overall parent use of strategies measured monthly from 12 (pre) to 18 months of age (post). Analyses 2.2a and 2.2b uses child sensitivity to social contingency (interaction ratio from a still-face procedure at pre-test) to moderate growth in child prelinguistic communicative acts from a

language sample measured monthly from 12 months (pre) to 18 months of age (post) (analysis 2.2a) as well as CSBS Total Scaled Scores at 18 months (post) (analysis 2.2b). In analyses 2.3a and 2.3b, child attention to spoken language (orienting time toward speech from a sequential looking preference procedure at pre-test) moderates the same two outcomes as in 2.2a and 2.2b (growth in child prelinguistic communicative acts, CSBS Total Scaled Scores).

Moderation. Moderation in clinical trials deals with differential effectiveness of intervention as a function of other independent variables. This is typically accomplished with interaction terms, which mathematically state that the effect of an intervention goes up with increases in specific covariates. We will employ all current standards for regressions using interaction terms, including variable centering, ⁹⁰ application of variance inflation factors to test for multicollinearity, ⁹¹ and residual diagnostics to ensure valid and interpretable estimates.

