Multiple-group SEM. Interaction can be further implemented via multiple-group SEM due to the fact that our predictor (intervention status) is a categorical variable. Intervention and control groups are specified as separate groups in a multiple-group SEM framework, and all model parameters can either be constrained to equality across groups to measure main effects or freed to test interactions and moderation. This method allows for both equivalence to extant moderation approaches and flexibility to test for differences in non-traditional parameters, specifically residual variance terms.

Aim 2 analytic plan. Analyses for Aim 2 will utilize SEM equivalencies of both traditional regressions and growth curve extensions of these models. Interaction terms will be centered and included in models as described below. We will estimate all models in SEM to minimize the impact of attrition.

Analysis 2.1. Intervention effects for parent use of communication support strategies will be moderated by parental communicative insightfulness (i.e, proportion of child communicative acts correctly identified by parents in the Communicative Insightfulness Assessment at pre-test). This model will be estimated exclusively using SEM as a latent parent growth variable with parent use of communication support strategies measured monthly from 12 months (pre) to 18 months of age (post) as the primary outcome.

Analysis 2.2a. Intervention effects on a latent slope representing growth in child prelinguistic communicative acts from a monthly language sample from 12 months (pre) to 18 months of age (post) will be moderated by child sensitivity to social contingency (interaction ratio from a still-face procedure) at 12 months of age (pre). This model will be estimated exclusively using SEM with a latent child growth variable of prelinguistic communicative acts, measured during monthly language samples from 12 to 18 months of age, as the primary outcome.

Analysis 2.2b. Intervention effects on observed CSBS Total Scaled Scores at 18 months (post) will be moderated by child sensitivity to social contingency (interaction ratio from a still-face procedure) at 12 months of age (pre). This analysis will be carried out jointly using regression methods for residual diagnostics and estimation of variance inflation factors and as a structural equation model, with the former used for assumption checking and robustness to missing data and the latter used for final scientific decisions.

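### The moderator named for analyses 2.2a and 2.2b, a still-face interaction ratio, matches no assessment in the protocol, and the nearest task has no stated score

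*SAP*

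**What the plan says.** **SAP, Aim 2 Analyses.** The overview gives one operational definition of child sensitivity to social contingency, the "interaction ratio from a still-face procedure at pre-test". The analytic plan repeats it for both 2.2a (growth in prelinguistic communicative acts) and 2.2b (CSBS score at post-test). In each, the intervention effect is to be "moderated by child sensitivity to social contingency (interaction ratio from a still-face procedure" at the pre-intervention time point.

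**Protocol, section 1.0.** The aims include "child (sensitivity to social contingency; attention to spoken language) moderators of intervention outcomes", so the construct is planned in both documents.

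**Protocol, section 8.0, Table 1.** No still-face procedure and no interaction ratio is listed. The Social Engagement Eye-Tracking Task, given at T0, has "two consecutive engagement conditions with animal hand puppets as the stimuli: (a) joint attention, (b) unavailable". In the first condition "the caregivers will respond only after the child vocalizes or gestures". For the second, the table says: "In the unavailable condition, the caregiver will read a book silently and will ignore all child communicative behavior". The entry describes how the task is run and names no score. It marks the task as lab-based and for Chicagoland participants only. Section 11.0 makes the eye-tracking visits an optional consent element, and section 10.0 says recruitment is both local and national.

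**SAP, Power Analysis.** Moderators are said to be detectable with 80% power if they explain 7.8% of outcome variance, and with 90% power at 10.4%.

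**The concern.** A moderator test counts as prespecified only if the moderator was fixed in advance. For 2.2a and 2.2b the instrument named in the SAP is not among the protocol's assessments, so the input variable cannot be traced to a data source.

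If the puppet task is the intended source, several scores remain possible. Gaze, vocalisations or gestures could be counted, and the two conditions could be compared as a ratio or as a difference. Each choice is a different moderator. If the choice were made after outcomes had been seen by arm, a selected interaction could be reported as a planned one.

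Naming the task also shows a coverage limit that the SAP does not mention: the moderator would be observed only in local families who opted in.

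**Working it through.** **Step 1. Trace each Aim 2 moderator to protocol Table 1.**

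| SAP analysis | Moderator measure in the SAP | Match in protocol Table 1 | Restricted to Chicagoland? |
|---|---|---|---|
| 2.1 | Communicative Insightfulness Assessment | Same name | Yes |
| 2.2a, 2.2b | Interaction ratio, still-face procedure | None by name; nearest is the Social Engagement task | Yes, for the nearest task |
| 2.3a, 2.3b | Orienting time toward speech | Attention to Speech vs Sine-Wave task, by content | Yes |

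Two of the five tests do not trace to a listed measure.

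**Step 2. Compare the nearest task with the construct.** The SAP describes sensitivity to social contingency as the child associating their own communication with the parent's responses. The Social Engagement task contrasts a caregiver who responds contingently with one who ignores the child, at T0. Construct and time point both fit. Three things are missing: the still-face label, a link to 2.2a/2.2b, and a score.

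**Step 3. Reproduce the stated moderator power.** Inputs from the SAP are R² = 0.078 and 0.104, 96 randomised, and 86 after 10% attrition. Two-sided alpha 0.05 is assumed because the SAP does not state alpha. The test is a 1-df F test for one added interaction term, with f² = R²/(1 − R²), noncentrality λ = N·f², and N − 5 denominator df (four predictors assumed; using one to five changes the power by no more than 0.1 point).

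- f² = 0.078/0.922 = 0.0846, and 0.104/0.896 = 0.1161.
- N = 96: λ = 8.12 and 11.14, giving power of 80.5% and 91.0%. This agrees with the stated 80% and 90%.
- N = 86: λ = 7.28 and 9.98, giving 76.0% and 87.7%. This does not agree.
- N = 86, one-sided: 84.8% and 93.2%. This does not agree either.

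The stated figures therefore behave as if all 96 dyads had the moderator measured.

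**Step 4. Power if only a subset has the moderator.** The documents do not give the Chicagoland share or the opt-in rate. The shares below are assumptions.

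| Assumed share of 96 | n | Power at 7.8% | Power at 10.4% |
|---|---|---|---|
| 100% | 96 | 80.5% | 91.0% |
| 75% | 72 | 68.2% | 81.3% |
| 50% | 48 | 50.4% | 63.6% |
| 25% | 24 | 27.3% | 35.4% |

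Taking the same shares of 86 instead (n = 64, 43, 22) gives 62.9%, 46.0% and 25.1% at 7.8%, and 76.5%, 58.6% and 32.6% at 10.4%.

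**The case against.** A reader might infer that the trial never collects this moderator and that 2.2a and 2.2b cannot be run at all. The documents do not support that. The protocol lists a baseline task with responsive and unresponsive caregiver conditions, from which a contingency score could plausibly be derived. Nothing in either document rules out that the interaction ratio was meant to compare those two conditions. What can be said is that the link is not stated.

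It is also fair that the SAP tends to describe tasks by paradigm while the protocol uses task titles. The 2.3 measure is described as a looking-preference procedure, a name that is not in protocol Table 1 either, yet its content identifies the task. The 2.2 mismatch is wider. A still-face label does not describe a caregiver reading silently during a puppet task, and no score is stated on the protocol side to connect the two.

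A reader might also infer that a substitute score was picked after the data were seen. Nothing in the documents shows this; it is a risk that the open definition leaves in place.

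Finally, the SAP fits all models by full information maximum likelihood, so dyads without the moderator need not be dropped. That stands as a point about who enters the model. It does not restore the stated power, because dyads whose moderator was never observed contribute little to estimating an interaction with it.

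**Conclusion.** The point holds as a mismatch of instrument and a missing score definition, affecting two of the five Aim 2 tests (2.2a and 2.2b). It does not hold as a claim that no usable data exist. The effects tested in Aims 1 and 3 and the mediation analyses of Aim 4 do not use this moderator.

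The coverage limit is broader than 2.2. The measures for all five moderator tests appear to be Chicagoland-only (for 2.2, if the Social Engagement task is the source), while the stated moderator power matches about 96 dyads. How far power falls depends on a share that the documents do not give. Over assumed shares of 75% to 25% of the 96, it is about 68% to 27% for a moderator explaining 7.8% of variance.

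This rests on two-sided alpha 0.05, on a single interaction term, and on the protocol text available, which lacks its figures and some pages.

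**What to change.** - In the SAP's Aim 2 overview and in analyses 2.2a and 2.2b, replace the still-face reference with the task actually given, and define one score with its formula. The choice of score belongs to the sponsor.
- Fix that definition before any outcome is examined by arm. If outcomes have already been examined by arm, report the choice as post hoc.
- State that the task, if it is the Social Engagement task, is lab-based, optional and Chicagoland-only, so the moderator is observed only in that subset. Say how dyads without it are handled under full information maximum likelihood. State the Chicagoland limit for 2.1 and 2.3a/b as well, so that two tests are not singled out.
- Restate the moderator power for the number of dyads with each moderator measured.

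The cost is a revision of SAP text and one recalculated power statement, with no new data collection. The downsides are that the moderator will be defined on a task other than the one the SAP now names, and that the moderator power will look less favourable than the present figures.
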